11.3 Early Termination of Patients from the Study

Patient participation in this study may be discontinued for any of the following reasons:

1. Occurrence of any medical condition or circumstance that exposes the patient to substantial risk and/or does not allow the patient to adhere to the requirements of the protocol.
2. If the patient clots the hemodialyzer or the dialysis circuit in the pre-treatment observation period (from Day -8 to Day 1 prior to dosing) at least twice during one HD session, they may be discontinued from the study at the discretion of the PI. If the patient repeatedly clots the hemodialyzer or dialysis circuit during each HD session, continuation of the patient in the study will be at the PI's discretion. However, available data obtained from such subjects will be included in the analyses.
3. Any SAE, clinically significant AE, severe laboratory abnormality, intercurrent illness, or other medical condition that indicates to the PI that continued participation is not in the best interest of the patient.
4. Patient's decision to withdraw.
5. Requirement of prohibited concomitant medication.
6. Patient failure to comply with protocol requirements or study-related procedures.
7. Termination of the study by the Sponsor, Food and Drug Administration (FDA), Celerion, CRU, or other regulatory authorities.
8. In the case of incomplete dosing (e.g., a large droplet of study medication on the surface of the skin) as deemed by the PI (or designee) and/or Sponsor.

The clinical report will include reason(s) for patient withdrawals as well as details relevant to the patient withdrawal.

If a patient is withdrawn from the trial prior to study completion, the patient will undergo all procedures scheduled for early termination as the situation allows (see the Study Events Flow Chart ([Section 6](#))). Any patient withdrawn due to an AE (whether serious or non-serious) or clinically significant abnormal laboratory test values will be evaluated by the PI or a monitoring physician and will be treated and/or followed up until the symptoms or values return to normal or acceptable levels, as judged by the PI or designee.

11.4 Study Restrictions

11.4.1 Prohibitions and Concomitant Medication

Consumption of foods and beverages containing the following substances will be prohibited as indicated:

- Xanthines/caffeine: 48 hours prior to dosing and throughout the period of sample collection (small amounts of caffeine derived from normal foodstuffs e.g., 250 mL/8 oz./1 cup decaffeinated coffee or other decaffeinated beverage, per day, with the exception of espresso; 45 g/1.5 oz. chocolate bar, per day, would not be considered a deviation to this restriction);
- Alcohol: 48 hours prior to dosing and throughout the period of sample collection;

Concomitant medications will be listed, recorded, and allowed except for those listed as prohibited in the exclusion criteria in [Section 11.2](#). It is understood and will be considered that treatment with certain drugs or cessation of treatment with certain drugs may have adverse effects and could interfere with the evaluation of the primary outcome measures of the study. Apart from anticoagulant/antiplatelet agents, no patient will be requested to stop taking any medication to be able to participate in the trial.

Acetaminophen (up to 2 g per 24 hours) or opioids may be administered, for fever or chronic pain control, at the discretion of the PI or designee. Administration of opioids for certain types of pain management may be allowed.

If deviations occur, the PI or designee in consultation with the Sponsor if needed will decide on a case-by-case basis whether the patient may continue participation in the study.

11.4.2 Meals

At the CRU, meals and/or snacks and fluids will be provided at appropriate times following check-in and throughout the study as per the clinical site standard procedure.

11.4.3 Activity

On Day 1, as dosing will be upon initiation of the HD session, patients will be dosed in the same position as required for their HD session. Patients will maintain that position for the whole HD session, as per standard HD procedure, except when they are supine or semi-reclined for other study procedures. At other times, there will be no specific activity restrictions. However, should AEs occur at any time, patients may be placed in an appropriate position.

Patients will be instructed to refrain from strenuous exercise which could cause muscle aches or injury, including contact sports at any time from 72 hours prior to check-in on Day -8 and throughout the study.

12. TREATMENTS

12.1 Treatments Administered

A separate pharmacy manual provided by the Sponsor will detail the preparation and treatment administration to be followed for this study.

E-WE thrombin will be supplied as a sterile, non-pyrogenic, preservative-free liquid for bolus and infusion.

E-WE thrombin will be supplied as 0.1 mg/mL, according to the planned dose ($\mu\text{g}/\text{kg}$) for each cohort, as noted below in [Table 2](#).

Matching placebo will be supplied as sterile formulation buffer for bolus and infusion.

Table 2. Investigational Products

Product	Description
Test	E-WE thrombin (0.1 mg/mL)
Placebo	Matching placebo for E-WE thrombin (16.2 mM sodium citrate, 3.8 mM citric acid, 150 mM sodium chloride, 0.1% polysorbate 80, at pH 6)

An unblinded pharmacist will be responsible for providing E-WE thrombin or matching placebo to the blinded study personnel for administration as per the randomization scheme.

Patients will be enrolled in Cohort 1 or Cohort 2. Within each cohort, patients will be randomized to active drug or matching placebo as summarized in [Table 1](#).

On Day 1, patients in each cohort will receive a single dose of E-WE thrombin or matching placebo as a bolus followed by an infusion into the dialysis line during a 4 hour HD procedure. Cohort 1 will be completed prior to initiation of Cohort 2.

Planned doses will be as follows:

Cohort 1: 0.5 $\mu\text{g}/\text{kg}$ bolus dose administered into the dialysis line immediately followed by a 0.25 $\mu\text{g}/\text{kg}/\text{hour}$ continuous infusion dose into the dialysis line over 4 hours of E-WE thrombin or matching placebo, for a total dose of 1.5 $\mu\text{g}/\text{kg}$.

Cohort 2: 1 $\mu\text{g}/\text{kg}$ bolus dose administered into the dialysis line immediately followed by a 0.5 $\mu\text{g}/\text{kg}/\text{hour}$ continuous infusion dose into the dialysis line over 4 hours of E-WE thrombin or matching placebo, for a total dose of 3 $\mu\text{g}/\text{kg}$.

Hour 0 will correspond to the beginning of E-WE thrombin bolus administration. The time of bolus administration and the times at which the infusion is started and stopped must be recorded.

The patient weight recorded at check-in will be used to calculate the study drug dose.

Should the need arise to change the infusion rate (i.e., due to an AE), changes to the infusion rate and the times at which those changes are made will be documented.

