10. INVESTIGATIONAL PLAN

10.1 Overall Study Design and Plan

This is a phase 2, randomized, double-blind, placebo-controlled, single-dose study of E-WE thrombin designed to evaluate the safety and efficacy at 2 dose levels administered to patients with ESRD during HD conducted at one study center in the US.

Patients will be enrolled in Cohort 1 or Cohort 2; cohorts will be dosed sequentially. Dosing of Cohort 2 will commence following completion of all study events for all patients in Cohort 1. Within each cohort, patients will be randomized to receive active drug or matching placebo as summarized below:

Table 1. Cohort and Treatment Randomization

Cohort	Treatment	Active:Placebo	Cohort Size
1	0.5 µg/kg bolus dose administered into the dialysis line immediately followed by a 0.25 µg/kg/hour continuous infusion dose into the dialysis line over 4 hours of E-WE thrombin or matching placebo, for a total dose of 1.5 µg/kg	2:1	12:6
2	1 µg/kg bolus dose administered into the dialysis line immediately followed by a 0.5 µg/kg/hour continuous infusion dose into the dialysis line over 4 hours of E-WE thrombin or matching placebo, for a total dose of 3 µg/kg	2:1	12:6

This study includes a screening period of 28 days prior to checking in to the CRU on Day -8. From Day -8 (8 days prior to dosing on Day 1) through Day 3, all patients will undergo HD 5 times and will be assessed for all scheduled procedures and endpoints before and after each HD session as per the Study Events Flow Chart ([Section 6](#)), using only one type of dialyzer cartridge for each patient.

On Day 1, prior to dosing, patients will undergo baseline measurements followed by initiation of a regular HD procedure, consistently using only one type of dialyzer cartridge for each patient. A single dose of E-WE thrombin or matching placebo will be administered into the dialysis line during the HD procedure. Patients will continue to undergo HD procedures and scheduled assessments from Day 1 through Day 3.

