12.2 Dose Modification

The dose and administration of the study drug to any patient within a cohort may not be modified. If necessary, a patient must be discontinued for the reasons described in [Section 11.3](#).

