Appendix 16.2.5.3 Test Compound Administration (Safety Population)

Subject Number	Cohort/ Treatment	Study Visit	Study Time	Date	Dose Administered?	Bolus Administration Time	Dosing Start Time	Dosing End Time	Route	Form	Frequency
X	1/A	Day 1	Hour 0	DDMMYYYY	Yes	HH:MM:SS	HH:MM:SS	HH:MM:SS	IV Infusion	Injection	Once

Note: Treatment: A = 0.5 µg/kg bolus dose of E-WE Thrombin followed by a 0.25 µg/kg/hour continuous infusion over 4 hours for a total dose of 1.5 µg/kg
B = 1.0 µg/kg bolus dose of E-WE Thrombin followed by a 0.5 µg/kg/hour continuous infusion over 4 hours for a total dose of 3.0 µg/kg
P = Placebo

Program: /AXXXXX/sas_prg/stsas/lis_PROGRAMNAME.sas DDMMYYYY HH:MM

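### Protocol Sections 12.1 and 12.2 conflict on changing the infusion rate because of an AE, and the SAP dosing listing shell would show a full stop but not a reduced rate

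*Protocol*

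**What the plan says.** **Protocol, Section 12.1** gives the planned bolus and infusion for each cohort and requires the bolus time and the infusion start and stop times to be recorded. It continues: "Should the need arise to change the infusion rate (i.e., due to an AE"), then "changes to the infusion rate and the times at which those changes are made will be documented". It sets no criterion for a change, does not call it a deviation, and does not refer to Section 12.2.

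**Protocol, Section 12.2** states: "The dose and administration of the study drug to any patient within a cohort may not be modified". It makes no exception for AEs. The alternative is: "If necessary, a patient must be discontinued for the reasons described in" Section 11.3.

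**Protocol, Section 11.3** lists reasons for which participation may be ended. Two are relevant: "Any SAE, clinically significant AE, severe laboratory abnormality, intercurrent illness, or other medical condition", where the PI judges that continuing is not in the patient's interest, and "In the case of incomplete dosing (e.g., a large droplet of study medication on the surface of the skin"). Neither mentions a change of rate.

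**SAP.** Section 5 labels the groups by planned total dose: 1.5 µg/kg, 3.0 µg/kg and pooled placebo. Section 4.1 admits to the Safety Population anyone who received study drug, and to the PD Population anyone who also has one postdose PD measurement. The dosing listing shell, "Appendix 16.2.5.3 Test Compound Administration (Safety Population"), has columns for bolus time, dosing start time and dosing end time. It has none for rate, time of rate change or amount delivered.

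**The concern.** If an AE occurs during the 4-hour infusion, Section 12.1 reads as though the rate may be changed and the change written down. Section 12.2 reads as though it may not, with discontinuation the only other course. Two members of staff could each follow the protocol and act differently. The primary objective is safety and tolerability, so this is the situation in which the instruction should be unambiguous.

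The analysis consequence is smaller. If a rate is changed, the patient receives something other than the planned total. The SAP states no rule for that case and derives no delivered dose. Section 8.3.2 of the protocol gives the infusion the task of sustaining the effect through the whole session, and clotting is graded at the end of the session. A reader of the clotting, APC-PCI or AE results would therefore want to know which patients had an altered infusion.

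**Working it through.** **1. The passages side by side**

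| Question | Section 12.1 | Section 12.2 | Section 11.3 |
|---|---|---|---|
| May the rate change for an AE? | Foreseen | Barred, with dose and administration both covered | Not mentioned |
| What follows? | Document the change and its time | Discontinue if necessary, under 11.3 | Participation may be ended; for AEs the PI judges |

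A change of infusion rate is a change of administration, so the same act is foreseen in one section and barred in the next. Both are current text, and neither refers to the other on this point.

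**2. The plan's own dose figures**

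Inputs are from Table 1 in protocol Section 10.1; Cohort 1, for example, starts with "0.5 µg/kg bolus dose administered into the dialysis line immediately followed by" an infusion of 0.25 µg/kg/hour. Total = bolus + rate × 4 h.

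- Cohort 1: 0.5 + 0.25 × 4 = 1.5 µg/kg, as stated.
- Cohort 2: 1 + 0.5 × 4 = 3 µg/kg, as stated.

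Infusion share = rate × 4 / total: 1.0/1.5 = 67% and 2.0/3.0 = 67%.

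**3. What a changed infusion would deliver**

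The documents give no size or frequency for rate changes. The cases below are assumptions that show the range.

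Stop at hour h: bolus + rate × h. Rate halved from hour h: bolus + rate × h + (rate/2) × (4 − h).

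| Assumed event | Cohort 1 (µg/kg) | Cohort 2 (µg/kg) | Share of plan |
|---|---|---|---|
| Stopped at 1 h | 0.75 | 1.5 | 50% |
| Stopped at 2 h | 1.0 | 2.0 | 67% |
| Stopped at 3 h | 1.25 | 2.5 | 83% |
| Halved from 1 h | 1.125 | 2.25 | 75% |
| Halved from 2 h | 1.25 | 2.5 | 83% |
| Halved from 3 h | 1.375 | 2.75 | 92% |

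**4. What the listing shell would show**

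Take two Cohort 2 patients, one stopped at 3 h and one halved from 2 h. Both receive 2.5 µg/kg: 1 + 0.5 × 3, and 1 + 0.5 × 2 + 0.25 × 2.

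- Stopped patient: the end time is one hour early. Bolus + planned rate × listed duration = 1 + 0.5 × 3 = 2.5, which is correct.
- Halved patient: start and end times span the full 4 hours. The same calculation gives 1 + 0.5 × 4 = 3.0, which is 0.5 µg/kg too high, and nothing in the listing shows it.

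Times alone are therefore enough for a stop but not for a reduced rate. With 12 active patients per dose level, one such patient is 1/12 = 8.3% of the group.

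**The case against.** The case on the other side has several parts.

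- **Section 12.1 only keeps records.** It authorises nothing and sets no criterion, so Section 12.2 could be taken as the sole rule and 12.1 as paperwork for departures. This does not remove the conflict: 12.1 names an AE as a foreseen reason and does not call the change a deviation.
- **The pharmacy manual may settle it.** Section 12.1 refers to a separate manual for administration, which is not among the documents. It may help staff, but it cannot cure two conflicting protocol rules.
- **The data may be listed anyway.** SAP Section 7 commits to listing everything on the CRF by patient, and Section 11 says the shells may not cover every aspect of the study. There are also listings for protocol deviations, PD exclusions and action taken for AEs. This stands: a missing column in a shell does not show that rate changes will go unreported. What is missing is a handling rule and a delivered-dose variable.
- **Grouping by assigned dose is legitimate.** This also stands. An AE that prompts a rate change began under the planned rate, and the analyses are descriptive.

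A reader might infer from the table that a Cohort 2 patient stopped at hour 1, with 1.5 µg/kg, is really a Cohort 1 patient under the wrong label. The documents do not support that. Such a patient had twice the Cohort 1 bolus and rate, and protocol Section 8.3.3 presumes a half-life of active drug of seconds to minutes, so equal totals are not equal exposure. The case is also a discontinuation, which Section 12.2 already allows and the listed times already show.

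**Conclusion.** The conflict between Sections 12.1 and 12.2 is real, and Section 11.3 does not resolve it. It bears on conduct during an AE, and the wording needs correcting whichever rule the clinical team chooses.

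The reporting gap is real but narrow. The part of the dose exposed to a rate change is two-thirds of the planned total in each cohort. Under the assumptions shown, halving the rate from hour 1, 2 or 3 delivers 75%, 83% or 92% of plan, and the dosing listing shell would not reveal it. A full stop would be visible.

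A reader might go further and conclude that results are attributed to doses not given, or that patients should be regrouped by delivered dose. The documents do not support either. No rate change is known to have occurred, its frequency cannot be estimated from the documents, and summaries by assigned dose are a sound choice. No stated power or sample-size figure is affected, since protocol Section 14.1 set the sample size without statistical considerations.

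**What to change.** 1. **Protocol.** Reconcile Sections 12.1, 12.2 and 11.3 so that one rule applies to an AE during the infusion. The clinical team decides which. Each section should refer to the others.
2. **SAP, if rate changes remain possible.** Keep all summaries by assigned dose, and say so. Add to Appendix 16.2.5.3 the rate in each segment and the time of each change.
3. **Delivered dose.** Derive it as bolus + Σ (rate × duration) over rate segments. A single rate multiplied by total time is wrong whenever the rate changes.
4. **Flag.** Mark patients whose delivered dose differs from plan, with any tolerance for small timing differences fixed before unblinding.

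The cost is an amendment to the protocol wording, a few listing columns, one derived variable and a flag. No new assessment is needed, because Section 12.1 already requires rate changes and their times to be documented. The derivation needs the rates as well as the times, so the sponsor should confirm that the CRF, which is not among the documents, captures both.

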12.2 Dose Modification

The dose and administration of the study drug to any patient within a cohort may not be modified. If necessary, a patient must be discontinued for the reasons described in [Section 11.3](#).

12.3 Method of Assigning Patients to Treatment Groups

Each patient will be assigned a unique identification number upon screening. Patients who complete the study screening assessments and meet all the eligibility criteria will be assigned a unique randomization identification number at the time of dosing, different from the screening number, and will receive the corresponding product, according to a randomization scheme generated at Celerion.

Patients will be enrolled in Cohort 1 or Cohort 2 with Cohort 1 to be completed prior to the initiation of Cohort 2.

In each cohort, an attempt will be made to enroll at least 50% of females and at least 30% of a race/ethnic minority group. An attempt will also be made to approximately match key characteristics, including sex, average age, and weight between cohorts.

In each cohort, patients will be randomized to receive either E-WE thrombin or matching placebo maintaining a 2:1 ratio

If replacement patients are used, the replacement patient number will be 100 more than the original (e.g., Patient No. 101 will replace Patient No. 1).

12.4 Blinding

This is a double-blind, placebo-controlled study.

12.4.1 Maintenance of Randomization

A computerized randomization scheme will be created by a Celerion statistician and it shall be considered blinded as per the following: the randomization is available only to the CRU pharmacy staff preparing the drug who will not be involved in any other aspect of the study including administration of the drug. It will not be made available to the Sponsor, patients, or members of the staff responsible for the monitoring and evaluation of safety assessments.

12.4.2 Procedures for Breaking the Blind Prior to Study Completion

One set of sealed envelopes containing the randomization code will be supplied to the PI or designee at the start of the study.

Breaking of the blind is expressly forbidden except in the event of a medical emergency where the identity of the drug must be known in order to properly treat the patient, or in the event of a safety interim analysis at the request of the Sponsor.

In the event of a medical emergency, it is requested that the PI or designee make every effort to contact the Study Monitor or designee prior to breaking the blind. If breaking the blind is required because of a medical emergency, the treatment identity would be revealed by the PI or designee, for that patient only. In the event that the emergency is one, in which it appears that the other patients may be at imminent risk, the blind may be broken for all patients dosed at that dose level. The unblinding will be properly documented in the study file.

In all cases where the code is broken, the PI or designee should record the date and reason for code breaking.

At the end of the study, envelopes will be retained or destroyed according to site procedures unless specified otherwise by the Sponsor.

12.4.2.1 Revealing of Randomization

In the absence of a medical emergency, the blinded randomization for this study will not be revealed until all data are entered in the database, edits checks are performed, queries closed, and the database is officially locked.

12.4.3 Treatment Compliance

A qualified designee (e.g. nurse) will be responsible for administering and monitoring the timed dose. Before and after the bolus/infusion dose, the qualified designee will visually inspect the syringe to ensure that the patient has received the entire dose. In the case of incomplete dosing, a few milliliters of blood could be drawn back into the dosing syringe and carefully reinjected to ensure administration of the complete dose; this will be reported.

13. STUDY ASSESSMENTS AND PROCEDURES

The Study Events Flow Chart ([Section 6](#)) summarizes the clinical procedures to be performed at each visit. Individual clinical procedures are described in detail below. Additional evaluations/testing may be deemed necessary by the PI or designee and/or the Sponsor for reasons related to patient safety.

For this study, the primary assessment is safety and tolerability. Safety will be determined by evaluating AEs (including HD vascular access site reactions), physical examinations, bleeding time from the HD vascular access sites, vital sign measurements, 12-lead ECGs, clinical laboratory parameters, including but not limited to, hematology, serum chemistry profile, coagulation, and urinalysis, as outlined in the Study Events Flow Chart ([Section 6](#)).

Any nonscheduled procedures required for urgent evaluation of safety concerns take precedence over all routine scheduled procedures.

13.1 Screening

Within 28 days prior to check-in on Day -8, medical history and demographic data, including name, sex, age, race, ethnic minority group, body weight (kg), height (cm), BMI (kg/m²) and history of tobacco use will be reported. Each patient will have a physical examination, vital sign measurements (heart rate, blood pressure, temperature, and respiratory rate), 12-lead ECG, and the laboratory tests of hematological, coagulation, hepatic and renal function and additional tests as noted in [Section 13.2.7](#).

